# 11 DATA COLLECTION

## **11.1 Data Collection Forms**

Health assessment data:

- The baseline demographic (gender, age, city), medical, medication and symptom data will be obtained using surveys/questionnaires.
- Daily recordings of AF/ventricular arrhythmia episodes will be obtained from the participants' pacemakers.
- Symptoms of fatigue, change in medication use, and unscheduled visits to health professionals for heart arrhythmias/episodes will be recorded via phone interviews.
- Continuous recordings of biological parameters (pulse rate, pulse rate variability, temperature) obtained by wearing smart watch sensors.

## Exposure data:

- Household characteristics will be assessed with the help of a questionnaire at the onset of the study.
- Real time location data will be assessed using personal smartphones application for The Global Positioning System (GPS), satellite-based navigation system installed in every smartphone.
- Real time location data from the GPS will be coupled with accelerometer data from smart wristwatches.
- Hourly central data on air pollutants, including; ambient concentrations of PM10, PM2.5, as well as meteorological factors (temperature and relative humidity).

• Outdoor and indoor PM and chemicals at participants' households.

### 11.2 Data Management

The study will be overseen and managed by the Medical School, University of Cyprus, under the supervision of the LIFE+ MEDEA principal investigator, [name].

All collected data, will be analyzed and discussed between LIFE+ MEDEA partners only by using codes to ensure that the anonymity of the participants is fully preserved.

## 12 PARTICIPANT RIGHTS AND CONFIDENTIALITY

Patients will be informed about the program and the data to be obtained through the information material that will provided with the consent form.

During the study, patients will have the opportunity to get any additional information on any subject that concerns them from the study personnel and or principal investigator (project coordinator) [name] whose contact information will be given to all participants during the recruitment process and will also be available on the program's website.

Also, any relevant conclusions resulting from the collected data analysis will be communicated to patients at the end of the program. This information will concern the better monitoring and forecasting of dust storms and the results of the interventions in order to reduce exposure of the population to DDS events.

## 12.1 Informed Consent Forms

A signed consent form will be obtained from each participant. The consent form will describe the purpose of the study, the procedures to be followed, and the risks and benefits of participation. A copy will be given to each participant and this fact will be documented in the participant's record.

## **12.2** Participant Confidentiality

## Administrative safeguards:

Data will be completely anonymized and encrypted prior to sending to the central database. The full record of Cypriot AF patients with names, addresses, and other personal information will be kept by the principal investigator, [name]

[name] at the Medical School of the University of Cyprus and only authorized personnel will have access to this data (LIFE MEDEA+ project scientist [name]). All data to be collected, will be analyzed and discussed between program partners only by using codes (a participant identification number (Participant ID, PID) to ensure that the anonymity of the participants is fully preserved and to maintain confidentiality.

#### Technical safeguards:

Electronic access to Cypriot patient data will require a user name and password that will only be held by authorized personnel. All computer entry and networking programs will be done using PIDs only. In addition, the Microsoft Azure storage platform that will be used for the purpose of data storage and backup, is Health Insurance Portability and Accountability Act (HIPAA) compliant, that establishes requirements for the use, disclosure, and safeguarding of individually identifiable health information.

The University of Cyprus has a policy that requires computer users not to leave computers unattended and not to exchange entry codes between them. Still, it is worth mentioning that after a few hours of non-use, the computer automatically turns off and locks again, requiring the use of the input code again.

In the event that a computer containing personal data is no longer used, the University of Cyprus will ensure that the data will either be transferred or destroyed.

#### Physical safeguards:

The Medical School of the University of Cyprus is housed at the Shiakolio Educational Center, a safe building on [name].

The building is protected internally and with the supervision of the surrounding area, on a daily basis with a 24-hour security guard. The guard checks all incoming people in the building.

Data that may be in print will be kept in a closet in the office of the Project Coordinator so that no unauthorized person has access to them.

All records will be kept in a locked file cabinet.

## 13 ETHICAL CONSIDERATIONS

The study has already obtained clearance from the Cyprus National Bioethics Committee. The intervention under study meets the criteria of the Helsinki declaration and follows the ICH/GCP and EC rules of good clinical practice. Data from individual countries will be completely anonymized and encrypted prior to sending to the central database.

There are no significant ethical considerations, since all necessary safeguards will be taken so that all participants do not face any risk and their personal data is protected. Participation will be on a voluntary basis and all participants will be able to withdraw at any point in the program.

## 14 COMMITTEES

## Steering Committee:

The Steering Committee will scrutinize the quality of the project performance and will act as a supervisory body to ensure that the work described in individual actions is carried out. The members of the steering committee will include the Project Coordinator, Project Manager, and the Leaders of all other project partners (Soroca Clinical Research Center, University of Crete, Cyprus University of Technology, E.n.A. Consulting, Department of Labor Inspection, Cyprus Broadcasting Corporation, Cyprus Department of Meteorology). The Steering Committees will be responsible for the:

- Decisions on technical roadmaps for the project and monitoring implementation;
- Provision of data for preparation of reports and deliverables to the Commission.

## External Advisory Committee:

The external advisory committee will be responsible to counsel the project and to help transform our results to policies. The advisory committee will consist of relevant regulatory authorities and interested stakeholders. There will be in total 30 members from all participating sites (Cyprus, Greece, Israel, i.e. ~10 members from each site).

## 16 SUPPLEMENTS/APPENDICES

I. Informed Consent Form Template

Mitigating the Health Effects of Desert Dust Storms Using Exposure-Reduction Approaches (MEDEA) project

Assessment of health outcomes in children with asthma (ACTION C.7) and in adults with atrial fibrillation (ACTION C.8) during DDS events (with vs without intervention measures)

Public Health Intervention Study

Statistical Analysis Plan

(April 2018)

1. Sample Size Determination and Power Calculations

Sample size calculations for the panel study of asthmatic children

Sample size calculations are based on expected changes in asthma symptoms measured by asthma control test (ACT), which is our primary health outcome. Childhood ACT has seven items and provides a score ranging from 0 (poorest asthma control) to 27 (optimal asthma control). A cut-off point of 19 indicates uncontrolled asthma. Previous studies have shown that a minimally meaningful change in the ACT score is ranging from 2 to 3 points (Voorend-van Bergen et al, 2014). To detect a statistically significant difference of 3 points, the minimum sample size needed in each of the 3 groups is 100 participants. This sample size calculation is assuming a level of 0.05 and a power of at least 80% to detect this difference between the comparison groups.

Sample size calculations for the panel study of atrial fibrillation (AF) patients

There are no studies that evaluated the reduction in AF burden attributed to reduction in exposure to ambient air pollution.

We assume that the mean AF burden in the control group will be 15%+/-15%. We conservatively estimated the expected intervention effect to be 20% of relative reduction in AF burden. This is translated into the reduction of AF burden by mean of 43 minutes per 24 hours. Group sample sizes of 108 and 216 achieve 81% power to show a difference in means when there is a difference of -3.0 between the null hypothesis mean difference of 0.0 and the actual mean difference of 3.0 at the 0.05 significance level (alpha) using a two-sided Mann-Whitney-Wilcoxon Test. These results are based on 2000 Monte Carlo samples from the null distributions: WeibullMS(15 15) and WeibullMS(15 15), and the alternative distributions: WeibullMS(15 15) and WeibullMS(12 15).

In our power calculations for the panel studies in asthmatic children and AF patients, the sample size included a dropout rate of 30%, which is an overestimation of the dropout rate observed in previous studies in Cyprus and countries of the region (15-20%). Thus, even if DDS events are 20-30% less we will have ample statistical power to detect a significant effect of each intervention.

2. Data Analyses

Analyses of health outcomes in asthmatic children

Our main outcome for the asthmatic children is the mean monthly change in ACT score. We will have 5 repeated measurements of ACT score per year for each participant and we can assess the effectiveness of each intervention to reduce asthma symptoms during DDS events.

Secondary outcomes will be repeated assessments of asthma medication use, unscheduled visits for asthma, forced expiratory volume in 1 second, peak expiratory flow, and FeNO. For the lung function parameters we will obtain at least three repeated observations for each subject within each group, and this will make possible to assess the health benefits of the intervention and attribute them to the assigned intervention.

Toward this end, we will apply the following regression mixed effects model:

EQUATION1

$$\begin{split} H_{ij} &= (\beta_o + \nu_{oi} + h_{oi}) + (\beta_1 + \nu_{1,i} + h_{1i}) * (T_{ij} + (1 - T_{ij}) SR_{ij}) * C_{ij} + \\ &\qquad (\beta_2 + \nu_{2i} + h_{2i}) * D_{ij} + \beta_3 * Temperature_{ij} \\ &\qquad + \sum_{m=1}^{M} \gamma_{1m} X_{1mi} + \sum_{n=1}^{N} \gamma_{2n} X_{2nj} + \sum_{p=1}^{P} \gamma_{3p} X_{3pij} + \epsilon_{ij} \\ &\qquad (\nu_{oj} \nu_{tj} \nu_{si} \nu_{di}) \sim [(0 \ 0 \ 0 \ 0), \sigma] \\ &\qquad (h_{oi}, h_{ti}, h_{si}, h_{di}) \sim [(0 \ 0 \ 0 \ 0), \sigma_{\Box}] \end{split}$$

In equation1, Hij is a measured health outcome e.g. ACT score or FEV1 for a subject i on time point j; $\beta 0$ and v0i are the fixed and subject-specific random intercepts, respectively; $\beta 0$ and v1i are the fixed and subject-specific random slopes for the exposure term, respectively; $\beta 0$ and v2i are the fixed and subject-specific random slopes for the physical activity term, Dij respectively; Temperatureij is the ground temperature on time point j corresponding to subject i; $\beta 3$ is the slope for temperature: xmi is the value of the mth spatial predictor corresponding to subject i; xnij is the value of the nth temporal predictor corresponding to subject i, and; xpij is the value of the pth spatial-temporal predictor corresponding to subject i on time point j. Finally, h0i, h1i are the subject-specific random intercepts, exposure slopes, and physical activity slopes, respectively, which are specific to control, intervention I1 and intervention I12 groups. The spatial, temporal and spatio-temporal covariates that we will consider for the health effects mixed-effects model are outlined below:

i) Time Activity Data; ii) House Characteristic Data; iii) Meteorological data: We will download weather data from the website of the National Climatic Data Center (NCDC, 2010). We will include weather variables such as temperature, relative humidity, wind speed, visibility, sea level pressure, and planetary boundary layer (PBL); iv) Normalized Difference Vegetation Index (NDVI): We will obtain these data from the U.S., NASA NDVI data from the MODIS sensor. For each subject, we will aggregate NDVI measurements to a 1x1 km grid and a 1-month average. Specifically, we will use the Terra satellite product ID of MOD13A3; v) Land use variables: We will consider nearby emissions of PM2.5, PM10, and NOx from point sources and traffic. For each subject j, we will estimate percent urbanism within a 1x1 km area. We will identify within a 5 km radius geographical predictors such as roads, major buildings, ports, airports, and water bodies using ArcGIS[®] and ArcMap[™] and; vi) Base air pollution emission information: For each home i, we will collect information about the location of small unregistered air pollution sources such as unpaved roads and commercial activities. We will obtain some of this information by analyzing Google Maps.

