#### 8.1 Sample size consideration

There are no studies that evaluated the reduction in AF burden attributed to reduction in exposure to ambient air pollution.

We assume that the mean AF burden in the control group will be 15%+/-15%. We conservatively estimated the expected intervention effect to be 20% of relative reduction in AF burden. This is translated into the reduction of AF burden by mean of 43 minutes per 24 hours.

Group sample sizes of 108 and 216 achieve 81% power to show a difference in means when there is a difference of -3.0 between the null hypothesis mean difference of 0.0 and the actual mean difference of 3.0 at the 0.05 significance level (alpha) using a two-sided Mann-Whitney-Wilcoxon Test. These results are based on 2000 Monte Carlo samples from the null distributions: WeibullMS(15 15) and WeibullMS(15 15), and the alternative distributions: WeibullMS(15 15) and WeibullMS(15 15).

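### The stated 81% power for AF burden is about 76% on the SAP's own inputs, depends heavily on an unjustified intervention-arm SD, and is not power for a difference in means

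*SAP*

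**What the plan says.** SAP section 1 (AF panel) and Protocol 8.1 share one power statement.

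- **Control group:** "We assume that the mean AF burden in the control group will be 15%+/-15"%.
- **Effect:** "We conservatively estimated the expected intervention effect to be 20% of relative reduction in AF burden". Both documents then express it on the mean scale: "This is translated into the reduction of AF burden by mean of 43 minutes per 24 hours".
- **Power:** "Group sample sizes of 108 and 216 achieve 81% power to show a difference in means", "at the 0.05 significance level (alpha) using a two-sided Mann-Whitney-Wilcoxon Test", from 2000 Monte Carlo samples.
- **Alternative in the SAP:** "the alternative distributions: WeibullMS(15 15) and WeibullMS(12 15").
- **Alternative in Protocol 8.1:** "the alternative distributions: WeibullMS(15 15) and WeibullMS(15 15"), the same distribution in both groups.

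The two numbers in each bracket are the mean and SD. Neither document says why the intervention SD stays at 15 when the mean falls to 12, or whether the reduction is meant to be proportional, constant or something else.

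The primary comparison is the two intervention groups pooled against control (Protocol 2.1), hence 216 against 108. Protocol 8.2.2 and the SAP's univariate section make t-tests and repeated-measures ANOVA the default for continuous variables. Mann-Whitney is the fallback when parametric assumptions fail.

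**The concern.** The plan fixes the effect only through the mean. A Mann-Whitney test does not compare means. It responds to the probability that a random control patient has a higher burden than a random intervention patient, and that depends on the whole distribution. Once the mean is set at 12, the intervention SD sets the Weibull shape, and the shape largely sets the power. One unexplained input therefore carries much of the planning figure.

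The 81% is the only power given for the primary comparison. If the trial is negative, readers will weigh that result against 81%. If the figure does not follow from its own inputs, and falls well below that under another plausible form of the same mean effect, a non-significant result would be over-read as evidence against the interventions. Calling the assumption conservative makes this more likely, because the documents show nothing that makes the SD choice conservative.

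**Working it through.** **Inputs.** n = 108 and 216; two-sided alpha 0.05; Mann-Whitney; control mean 15, SD 15; intervention mean 12, SD 15 (all SAP section 1). Check of the mean effect: 0.20 × 15% × 1440 min = 43.2 min per day, which agrees with the plan.

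**Step 1: Weibull parameters.** Solve (SD/mean)² = Γ(1+2/k)/Γ(1+1/k)² − 1 for the shape k, then scale = mean/Γ(1+1/k).

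| Mean, SD | Shape | Scale | Median | 99th percentile |
|---|---|---|---|---|
| 15, 15 | 1.00 | 15.0 | 10.4 | 69.1 |
| 12, 15 | 0.81 | 10.65 | 6.8 | 70.8 |
| 12, 12 | 1.00 | 12.0 | 8.3 | 55.3 |

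Under (12, 15) the group mean falls 20% but the group median falls 35% (10.4 to 6.8). Under (12, 12) every quantile falls 20%.

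**Step 2: the plan's own figure.** With 20,000 simulated trials per run, the SAP inputs give 76 to 77%. Analytic check: z = (P − 0.5)/√[(N+1)/(12·n₁·n₂)], where P is the probability that a control value exceeds an intervention value. The denominator is √[325/(12 × 108 × 216)] = 0.0341. With P = 0.590, z = 0.090/0.0341 = 2.64 and power = Φ(2.64 − 1.96) = 75%.

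The gap to 81% is not simulation noise. The standard error with 2000 samples is √(0.81 × 0.19/2000) = 0.9 points, and sixty runs of 2000 samples ranged from 74.1% to 79.6%. Continuity correction, rounding, capping at 100% and swapping the groups all leave it at about 76%. An equal split of the same 324 patients (162 v 162) gives 80 to 81%. That may be where the figure came from, but the documents do not say so.

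The alternative printed in Protocol 8.1, with no difference between groups, gives about 5%.

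**Step 3: sensitivity to the effect model (Mann-Whitney, 108 v 216).**

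| Intervention distribution | Power |
|---|---|
| Weibull mean 12, SD 15 (SAP) | 76% |
| Weibull mean 12, SD 14 | 64% |
| Weibull mean 12, SD 13 | 51% |
| Weibull mean 12, SD 12 (proportional) | 37% |
| Control values minus 3, floored at zero (mean 12.3, SD 14.7) | 77 to 78% |

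Analytic check of the proportional case: both distributions are exponential, so P = 15/(15 + 12) = 0.556, z = 0.0556/0.0341 = 1.63 and power = Φ(−0.33) = 37%.

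**Step 4: detectable proportional reduction.** A 32% reduction has mean 10.2, P = 15/25.2 = 0.595, z = 2.79 and power 80%. A 33% reduction has mean 10.05, P = 0.599, z = 2.90 and power 83%. About 80% power therefore needs a proportional reduction of about 32 to 33%.

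**Step 5: is it a test of means?** Set both means to 15 and apply only the shape change (SD 15 v 18.75, since 18.75/15 = 15/12 gives shape 0.81). Mann-Whitney rejects about 22% of the time and Welch's t-test about 5%.

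t-test power for the mean difference itself:
- (15, 15) v (12, 15): SE = 15 × √(1/108 + 1/216) = 1.768; 3/1.768 = 1.70; Φ(1.70 − 1.96) = 40%. Simulation gives 39 to 41%.
- (15, 15) v (12, 12): SE = √(225/108 + 144/216) = 1.658; 3/1.658 = 1.81; Φ(1.81 − 1.96) = 44%. Simulation gives 43% (Welch) and 49% (pooled variance).

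**The case against.** The strongest reply is that the SAP does simulate a 20% reduction. The mean falls from 15 to 12, exactly 20%, and the plan states its effect as 43 minutes of mean burden. It never says that each patient's burden is multiplied by 0.8. An SD near 15 is also coherent: if every patient lost about the same amount, the SD would hardly change, and the floored 3-point reduction gives 77 to 78%. Nor is SD 15 an upper limit, since mean 12 with SD 16 gives about 85%. The documents say that no earlier studies exist, so nothing in them favours SD 12 over SD 15. The planned daily repeated-measures models may also perform differently from a single rank test.

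All of this stands, and it rules out three stronger readings that a reader might infer:

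- **That (12, 15) contradicts the named effect.** It does not. It is one way of producing it.
- **That the true power is 37%.** This holds only under proportional scaling, which the documents do not state.
- **That low-burden patients lose about half their AF and high-burden patients lose none.** The quantiles describe two parallel groups, not changes within patients. Reading them as individual effects requires that patients keep their rank order, which the plan does not assume.

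The reply does not rescue the 81%, which fails on the SAP's own inputs. It does not supply a reason for the SD, and it does not turn a rank test into a test of means. The repeated-measures models have no power calculation in either document, so they cannot support the 81%.

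**Conclusion.** Wrong as written, on three counts.

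1. The SAP's inputs give about 76%, not 81%, at 108 v 216.
2. The figure rests on an unjustified intervention SD. With the mean held at 12, moving the SD from 15 to 12 moves power from about 76% to 37%, roughly 40 points.
3. The claim "achieve 81% power to show a difference in means" does not describe a Mann-Whitney test. For a difference in means, t-test power is about 39 to 41% with (12, 15) and 43 to 49% with (12, 12). The t-test matters here because it is the plan's default for continuous variables.

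These figures assume Weibull burdens, one summary value per patient, 324 patients analysed and an unadjusted two-group test. The shift scenario replaces the Weibull form for the intervention group only. The 37% is one scenario, to be reported beside the others and not in place of them.

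**What to change.** In both SAP section 1 and Protocol 8.1:

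1. Restate the power for WeibullMS(15 15) v WeibullMS(12 15) at 108 v 216 as about 76%, or give the group sizes and settings that produced 81%.
2. State the intended effect model (proportional, constant or other) and justify the intervention-arm SD.
3. Report the proportional alternative, (15 15) v (12 12), beside it: about 37% power for a 20% reduction, or about 80% power only for a reduction of about 32 to 33%.
4. Remove the reference to means from the Mann-Whitney statement, or quote t-test power of about 40% for that claim.
5. Reconcile the alternative in Protocol 8.1, which shows no difference, with the one in the SAP.

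The cost is a re-run of the simulation and new wording in two documents. No patients are added. The downside is that the stated power becomes less favourable.

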## Assessment of health outcomes:

- Daily recordings of AF/ventricular arrhythmia episodes from the participants' pacemakers during the 4-month study period will be downloaded with interrogation of the pacemaker during a visit to the Arrhythmia Clinic after the end of the monitoring period.
- Phone interviews every 1 month throughout the high DDS period recording symptoms of fatigue, change in medication use, and unscheduled visits to health professionals for heart arrhythmias/episodes.
- Continuous recordings of biological parameters (pulse rate, pulse rate variability, temperature) will be obtained by wearing smart watch sensors that will be uploaded on line to e-platform.

Primary health outcome will be every detected high atrial frequency episode of >330 ms (180 beats per minute) lasting for longer than 30 s with an atrial sensitivity of 0.5 mV (assumed as an episode of AF). AF burden is defined as the overall time percentage with AF during the observed period. For the primary analysis, we will compare the combined effect in the two intervention groups versus the control group. Secondarily, the effectiveness of each intervention will be compared versus the control group and to each other.

Secondary health outcomes will be the occurrence of ventricular arrhythmias assessed through the pacemaker and heart rate variability.

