# 4 STUDY DESIGN

Type of study: Randomized clinical trial (Behavioural Intervention)

Patients with AF will be recruited during DDS outbreaks and will be randomized into three parallel groups to receive:

- a) No intervention for DDS,
- b) Intervention for outdoor exposure reduction, and
- c) Interventions for both outdoor and indoor exposure reduction.

Disease-related adverse health outcomes will be assessed in all the parallel arms of the study.

Previous publications of the MEDEA partners (Achilleos et al, 2014; Gerasopoulos et al, 2006; Krasnov et al, 2014), indicated that 2/3 of each year's DDS events in the Eastern Mediterranean region appear during February-May, with 10-15% of the days during this period being "DDS days". Thus we will perform this public health intervention study during February–May of 2019 and 2020.

Study population and location: Men and women with prior implantation of a dual lead (atrial and ventricular) pacemaker or ICD, will be recruited from the cardiac arrhythmia clinic at the Nicosia General Hospital of Cyprus (n=156) in project years 2018-2019 and 2019-2020. Each patient will have assessment of health outcomes during only one high DDS period.

Duration of the study: A feasibility trial and refinement of protocols and tools will be performed in the high DDS period of 2018. In the fall of 2018 and 2019, MEDEA personnel will start recruitment efforts to detect eligible AF patients for participation in the study during the high DDS periods of February-May 2019 and 2020.

Assessment of health outcomes:

- The occurrence of AF/ventricular arrhythmia episodes will be recorded daily using the already implanted participants' pacemakers or ICD during the 4-month study period. The recorded episodes will be downloaded with interrogation of the pacemaker or ICD during a visit to the Arrhythmia Clinic after the end of the study period.
- Phone interviews every 1 month throughout the high DDS outbreaks season will be carried out. Data collected will include symptoms of fatigue, change in medication use and unscheduled visits to health professionals for heart arrhythmias/episodes.
- Continuous recordings of biological parameters (pulse rate, pulse rate variability and temperature) obtained by wearing smart watch sensors and uploaded on line to the secure e-platform.

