## Figure C8.1. Study Year 1 (February-May 2019) - 78 patients with AFIB in each study site (Beer Sheba-Israel, Nicosia-Cyprus & Heraklion-Crete) to be randomized to three levels of intervention

### Life+ MEDEA Action C7 Protocol, Version 1.0

## 6.2 Handling of Study Interventions

A bidirectional, patient-centered e-Platform will be created to:

- Communicate promptly forecast alerts to individuals about upcoming DDS events through smartphone applications and text messaging
- Disseminate exposure reduction guidelines

In particular, in the group where there will be intervention for outdoor exposure reduction, the intervention will be carried out by:

- Informing the participant for upcoming desert dust storm episodes.
- Simultaneous transmission of instructions to patient's smartphone to reduce outdoor exposure during the episode (stay indoors, avoid intense physical activity outdoors, avoid competitive sports, avoid unnecessary walks).

In the group where there will be interventions for outdoor and indoor exposure reduction, the intervention will be carried out by:

- Informing the participant for upcoming desert dust storm episodes.
- Simultaneous transmission of instructions to patient's smartphone to reduce a) outdoor exposure during the episode (stay indoors, avoid intense physical activity outdoors, avoid competitive sports, avoid unnecessary walks), and b) indoor, home exposure (closed windows and doors, sealing possible cracks around windows and doors in order to minimize home ventilation, and using an air cleaner in order to filter indoor air).

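### SAP section 1 does not support ample power for each AF intervention with 20-30% fewer dust events: the calculation has no DDS-day input and covers only the pooled comparison

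*SAP*

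**What the plan says.** The AF calculation appears in Protocol 8.1 and SAP section 1. Control AF burden is assumed to be 15% with SD 15%. The effect is described thus: "We conservatively estimated the expected intervention effect to be 20% of relative reduction in AF burden". Both documents say that no earlier study has estimated this effect, and both translate it into 43 minutes per 24 hours. The result is "Group sample sizes of 108 and 216 achieve 81% power to show a difference in means", by a two-sided Mann-Whitney-Wilcoxon test at 0.05. The 108 and 216 are the control arm and the two intervention arms combined, which is the primary comparison. Each intervention against control is secondary and has no stated power.

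SAP section 1 then says that "the sample size included a dropout rate of 30%, which is an overestimation of the dropout rate observed in previous studies" (15-20%), and draws its conclusion from that: "Thus, even if DDS events are 20-30% less we will have ample statistical power to detect a significant effect of each intervention".

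Three other statements bear on this:

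- Outcome window: "AF burden is defined as the overall time percentage with AF during the observed period", with "Daily recordings of AF/ventricular arrhythmia episodes from the participants' pacemakers during the 4-month study period" (Protocol Summary).
- Timing of the intervention: "Simultaneous transmission of instructions to patient's smartphone to reduce outdoor exposure during the episode" (Protocol 6.2).
- Frequency of dust: Protocol section 4 describes February-May "with 10-15% of the days during this period being" DDS days.

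**The concern.** The SAP's conclusion concerns the number of dust events and the separate interventions. Its premise concerns dropout in a pooled comparison. The two are linked only by a connecting word.

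Fewer dropouts raise the number analysed. They do not add dust days, and they do not enlarge the effect in any patient. The inputs are a mean, an SD, a relative reduction, group sizes, a significance level and a test. No DDS-day count, share, burden ratio or carry-over appears, so robustness to 20-30% fewer events cannot be derived from them. The calculation also says nothing about 108 against 108.

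What is at stake is how a null result is read. Someone relying on this sentence would take no difference for one intervention, or in a season with little dust, as informative evidence against benefit. The trial is meant to inform public-health policy, so that reading matters.

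**Working it through.** **Inputs.** Control mean 15, SD 15; reduction 3.0 points (20% of 15; 0.03 x 1440 = 43.2 minutes); Weibull (mean, SD) 15,15 against 12,15 as printed in the SAP; two-sided 0.05; 1:1:1 allocation; 468 recruited, so 156 per arm; 108 per arm analysed. Dropout of 20% leaves 156 x 0.80 = about 124 per arm, and 15% leaves 156 x 0.85 = about 133.

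**Step 1: the plan's own figure.** Simulating the Mann-Whitney test (20,000 replicates) at 108 against 216 gives about 76%, not 81%. The null rejection rate is 5%. An equal split of the same 324 patients (162 against 162) gives about 81%. This is a separate point and the figure should be rerun. Both bases are therefore shown below: simulated, and rescaled from the stated 81%.

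**Step 2: rescaling formula.** A power of 81% implies a standardised effect of 1.960 + 0.878 = 2.838 at 108/216. At n against n, multiply by sqrt[(1/108 + 1/216)/(2/108)] = 0.866 and by sqrt(n/108). For a proportionate loss of effect q:

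per-arm power = Φ(2.838 x 0.866 x sqrt(n/108) x (1 - q) - 1.960).

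At n = 108 and q = 0 this is Φ(2.458 - 1.960) = Φ(0.498) = 69%.

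**Step 3: each intervention against control, full 3.0 points, no dust shortfall.**

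| Per arm | Dropout | Simulated | Rescaled from 81% |
|---|---|---|---|
| 108 | 30% (planned) | 64% | 69% |
| 124 | 20% | 70% | 75% |
| 133 | 15% | 72% | 78% |
| 156 | none | 79% | 84% |

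About 160 per arm is needed for 80% by simulation.

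**Step 4: 20-30% fewer events.** ASSUMPTION, not in the documents: the seasonal effect shrinks in proportion to the number of events. The reduction becomes 3.0 x 0.80 = 2.4 to 3.0 x 0.70 = 2.1 points.

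| Comparison | Simulated | Rescaled from 81% |
|---|---|---|
| Per arm, 108 vs 108 | 35-45% | 40-50% |
| Per arm, 133 vs 133 | 42-52% | 48-59% |
| Pooled, 108 vs 216 | 44-57% | 51-62% |
| Pooled, 133 vs 265 | 53-65% | about 60-71% |

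**Step 5: sensitivity to SD.** The simulated figures keep SD at 15 while the mean falls, as the SAP does. If SD fell to 12 with the mean, power at the full 3.0 points would be about 37% pooled and about 30% per arm. The ranges above are not bounds.

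**Step 6: what a 20% seasonal reduction requires.** Let g be the share of DDS days and R the ratio of AF burden on DDS days to other days. If all AF on DDS days were abolished and nothing changed on other days, gR/(gR + 1 - g) = 0.20, so R = 0.25(1 - g)/g. This gives R = 2.25 at g = 10% and R = 1.42 at g = 15%. Neither document states R.

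**The case against.** The strongest reply is that the seasonal comparison is not the only analysis. The SAP also plans daily repeated-measures, case-crossover and Poisson models. In these, fewer events could reduce the information rather than the effect per dust day, and extra patients would partly offset that. Assuming information scales with patients times events, the SAP's premise leaves (0.80 to 0.85)/0.70 x (0.70 to 0.80) = 0.80 to 0.97 of the planned information. Rescaling 81% by the square root of that gives 72-80% pooled and 59-68% per arm. The loss is smaller, but per-arm power still stays below 80%. Seasonal burden is also the endpoint that was powered.

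A second reply is that the 20% may hold whatever the dust count. The pooled comparison would then keep its 76-81%. The sentence speaks of each intervention, however, so Step 3 still applies.

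A reader might infer from the 10-15% DDS-day share that a 20% seasonal reduction is out of reach. The documents do not support that. It requires equal burden on all days, whereas the trial supposes that dust worsens AF. It also requires no effect beyond DDS days. Alerts follow forecasts and may cover more days, and the documents do not say whether indoor measures such as sealing cracks stay in place between episodes. The SAP also mentions anthropogenic pollution episodes. The missing input is certain; the size of any dilution is not.

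**Conclusion.** The SAP's claim does not hold for the AF panel. It fails without any assumption about dust: at the 15-20% dropout it relies on, power for each intervention with the full 20% granted is 70-72% simulated, or 75-78% if 81% is accepted. The SAP works to at least 80% elsewhere in the same section. Only with no dropout at all, and only on the rescaled basis, does per-arm power pass 80% (84%).

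The lower figures in Step 4 depend on proportional scaling and illustrate what the omitted input could do. It would go too far to conclude that the trial as a whole has power near or below 50%. That description fits the per-arm comparisons under the scaling assumption better than the primary pooled one, which is 53-65% at 15% dropout under the same assumption.

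Calling the 20% conservative has no stated basis, but it is not shown to be wrong. The SAP sentence also covers the asthma panel, which was not checked here.

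**What to change.** 1. Withdraw the SAP section 1 sentence for the AF panel. Otherwise, replace it with a calculation that shows each intervention against control separately and takes the DDS-day (or alert-day) share as an input, with assumptions and range stated.
2. In Protocol 8.1 and SAP section 1, state the DDS-day share and burden ratio under which a 20% seasonal reduction is reached. Drop the description of the effect as conservative unless it can be supported.

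The cost is wording, a short power table and a less favourable stated power. No change to data collection is needed.

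Optional: a secondary randomised comparison of AF burden on DDS days plus a stated lag, for example through a group-by-DDS term in the planned daily hierarchical model. That model now counts episodes rather than burden, so it would need adapting. The comparison would answer a useful question, but it would not repair the power statement.
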